8.1.3. Tumor Definitions

The following definitions are outlined according to RECIST 1.1 criteria:

Measurable Lesions: Only measurable lesions can be selected as target lesions.

- Measurable visceral lesions: Lesions that can be accurately measured in at least 1 dimension with the longest diameter (to be recorded) ≥ 10 mm by CT scan if using slice thickness of ≤ 5 mm, or at least double the slice thickness of the CT or MRI scan if the slice thickness is >5 mm.
- Measurable pathological lymph nodes: A malignant lymph node must be considered pathologically enlarged with high suspicion of metastasis and measure ≥ 15 mm in the short axis when assessed by CT scan. The short axis is defined as the longest linear dimension perpendicular to the node's longest diameter as assessed within the same plane that the scan was acquired.

Non-measurable Lesions: All non-measurable lesions can only be selected as non-target lesions.

- Small visceral metastatic lesions that have a longest dimension <10 mm, or if slice thickness is >5 mm, less than twice the slice thickness
- Abnormal and suspected metastatic lymph nodes that are ≥ 10 mm to <15 mm in the short axis
- Truly non-measurable lesions (eg, ascites and peritoneal carcinomatosis)

Target Lesions:

- All measurable lesions up to a maximum of 2 lesions/organ and 5 lesions in total, representative of all involved organs/tissues should be identified as target lesions
- Target lesions should be selected on the basis of their size (visceral lesion with the longest diameter and lymph node with the measurement of short axis), be representative of all involved organs/tissues, but in addition should be those that lend themselves to reproducible repeated measurements
- When recording tumor measurements, the longest diameter will be measured for each non-nodal target lesion. For measurable pathological lymph nodes that may be identified as target lesions, the short axis measurement will be combined with the measurements of non-nodal (ie, visceral lesion) target lesions. Therefore, in cases of CR when abnormal nodes have been used as target lesions, the sum of diameters will not reduce to a null value.
- Target lesions will be followed up and measured at each subsequent timepoint.
- The sum of the diameters for all target lesions will be calculated and recorded. The baseline sum will be used as a reference to further characterize any objective response assessment in the measurable dimension of the disease.
- Assign a measurement to all target lesions regardless of size. An option of "too small to measure" will be provided if a measurement cannot be assigned. A value of zero should only be assigned in the case of a CR.

- An option of “not assessable” for a lesion will only apply to lesions that cannot be read due to technical reasons including:
 - CT artifact
 - Patient positioning where the lesions are obstructed or cannot be seen
 - Lesions that may not be seen in their entirety due to CT slice thickness
- In cases where a lesion divides into 2 lesions, the longest diameters of the fragmented portions should be added together to calculate the target lesion sum.
- In cases where 2 lesions coalesce, a plane between them may be maintained that would aid in obtaining maximal diameter measurements of each individual lesion. If the lesions have truly coalesced such that they are no longer separable, the vector of the longest diameter in this instance should be the maximal longest diameter for the “coalesced lesion.”

Non-target Lesions:

- Non-target lesions include all non-measurable lesions and measurable lesions that have not been selected as target lesions.
- The primary lesion should always be classified as a non-target lesion irrespective of its size and whether or not it can be accurately measured.
- Lymph nodes that have a short axis <1 mm are considered non-pathological and should not be recorded.
- Any equivocal lesion without clear diagnosis (eg, uncharacteristic solitary lung nodule without biopsy, uncharacteristic thyroid mass lesion without fine needle aspiration) may be considered a non-target lesion if it cannot be differentiated from a benign lesion.
- All other lesions (or sites of disease), including pathological lymph nodes, should be identified as non-target lesions and should also be recorded at Baseline. Measurements are not required, but their presence, absence, or unequivocal progression should be followed throughout the study.
- It is possible to record multiple non-target lesions involving the same organ as a single item on the eCRF (eg, multiple enlarged pelvic lymph nodes or multiple liver metastases).

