4.1. Inclusion Criteria

A patient must meet all of the following inclusion criteria to be eligible for participation in this study:

1. Provide documented informed consent (refer to Section [6.3](#))
2. ≥ 18 years of age (or meets the country's regulatory definition for legal adult age, whichever is greater)
3. Eastern Cooperative Oncology Group (ECOG) performance status 0 or 1
4. Has recovered from the acute toxic effects of prior anticancer therapy to baseline or Grade 1 (except toxicities which are not clinically significant such as alopecia)
5. Known *FGFR* aberration status and tumor type that meet all of the criteria for one of the following cohorts:

a. Cohort A

- i. Histologically confirmed, locally advanced, advanced, or metastatic solid tumors harboring a *FGFR1-4* rearrangement determined in tumor tissue using next-generation sequencing (NGS), fluorescence in situ hybridization (FISH), or other assays that can determine gene rearrangements in tumor tissues. Patients with primary brain tumor or iCCA are not eligible.
- ii. Measurable disease per RECIST 1.1
- iii. Had disease progression/recurrence after standard treatment for their advanced or metastatic cancer

b. Cohort B

- i. Histologically confirmed, locally advanced, advanced, or metastatic gastric or GEJ adenocarcinoma harboring a *FGFR2* amplification. The tumor must have an *FGFR2/CEN10* ratio of ≥ 5 or an *FGFR2* copy number ≥ 10 signals per cell determined in tumor tissue using NGS, FISH, or other assays that can determine gene amplifications in tumor tissues.
- ii. Measurable disease per RECIST 1.1
- iii. Received at least 2 prior systemic regimens for advanced/metastatic disease
- iv. Experienced disease progression/recurrence during or after the most recent prior systemic treatment for advanced/metastatic gastric or GEJ cancer.

c. Cohort C

- i. Confirmed MLN with a *FGFR1* rearrangement as defined by WHO criteria
- ii. Not a candidate for hematological stem cell transplant (HSCT) or relapsed after HSCT and donor lymphocyte infusion, and progressed and not a candidate for other therapies.
6. Has archival or fresh tumor tissue (preferably in block format) for Cohorts A and B and bone marrow tissue for Cohort C available to send to central laboratory.

7. Adequate organ function as defined by the following criteria:

a. Cohorts A and B:

- i. Absolute neutrophil count (ANC) $\geq 1.0 \times 10^9/L$
- ii. Platelet count $\geq 75,000/mm^3$ ($\geq 75 \times 10^9/L$)

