8.1.4.1. Target and Non-Target Response Assessments

Assessments will be based on the definitions for target and non-target lesions described in [Table 11](#).

Table 11: Target and Non-target Lesions

TARGET LESIONS	
Lesions Response:	Definition:
Complete Response (CR)	Disappearance of all target lesions. Any pathological lymph node must have reduction in short axis to <10 mm
Partial Response (PR)	At least a 30% decrease in the sum of diameters of the target lesions, taking as a reference the baseline sum diameters
Progressive Disease (PD)	At least a 20% increase in the sum of diameters of the target lesions, taking as a reference the smallest sum on study, including the baseline sum. In addition to the relative increase of 20%, the sum must also demonstrate an absolute increase of at least 5 mm. Definitive new lesion presence also indicates progression.
Stable Disease (SD)	Neither sufficient shrinkage to qualify for PR nor sufficient increase to qualify for PD, referencing the smallest sum diameters while on study.
NON-TARGET LESIONS	
Lesions Response:	Definition:
Complete Response (CR)	Disappearance of all non-target lesions and normalization of tumor marker level. All lymph nodes must be non-pathological in size (<10-mm short axis)
Partial Response (PR)	Persistence of one or more non-target lesion(s) and/or maintenance of tumor marker level above the normal limits
Progressive Disease (PD)	Unequivocal progression of existing non-target lesions (see following definition).

Abbreviations: CR=complete response; PD=progressive disease; PR=partial response; SD=stable disease

Progression in Non-target Disease: There must be an overall level of substantial worsening in non-target disease such that, even in the presence of SD or PR in target disease, the overall tumor burden has increased sufficiently to merit discontinuation of therapy.

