8.1.5. Objective Response Assessment

Assessments will be based on the definitions provided in [Table 12](#) and [Table 13](#). Since this is a non-randomized study, all responses (CR/PR) must be confirmed.

Table 12: Time Point Response for Patients with Target (\pm Non-target) Disease

Target Lesions	Non-Target Lesions	New Lesions	Objective Response
CR	CR	No	CR
CR	Non-CR/Non-PD or Not all evaluated	No	PR
PR	Non-PD or Not all evaluated	No	PR
SD	Non-PD or Not all evaluated	No	SD
Not all evaluated	Non-PD	No	NE
PD	Any	Yes or No	PD
Any	PD	Yes or No	PD
Any	Any	Yes	PD

Abbreviations: CR=complete response; NE=not evaluable; PD=progressive disease; PR=partial response; SD=stable disease

Table 13: Time Point Response for Patients with Only Non-target Disease

Non-Target Lesions	New Lesions	Objective Response
CR	No	CR
Non-CR/Non-PD	No	SD
Not all evaluated	No	NE
Unequivocal PD	Yes or No	PD
Any	Yes	PD

Abbreviations: CR=complete response; NE=not evaluable; PD=progressive disease; PR=partial response; SD=stable disease

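### Under the always-non-target rule in Protocol 8.1.3, a patient whose only measurable lesion is the primary can enrol but can never be scored PR

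*Protocol*

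**What the plan says.** Protocol 8.1.3 (Tumor Definitions) has two bullets that bear on a measurable primary. Under Target Lesions, the lesions to be identified as targets are "All measurable lesions up to a maximum of 2 lesions/organ and 5 lesions in total", chosen to represent every involved organ; the primary is not mentioned. Under Non-target Lesions: "The primary lesion should always be classified as a non-target lesion irrespective of its size and whether or not it can be accurately measured". The bullet just before that one reads: "Non-target lesions include all non-measurable lesions and measurable lesions that have not been selected as target lesions".

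Response follows from this classification. In Table 11 (8.1.4.1), target-lesion PR is "At least a 30% decrease in the sum of diameters of the target lesions", relative to baseline. Section 8.1.5 then gives two tables. Table 12 is for patients with target lesions; its PR row asks only that the non-target status be "Non-PD or Not all evaluated". Table 13, headed "Time Point Response for Patients with Only Non-target Disease", offers CR, SD, NE and PD.

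Entry to Cohorts A and B (4.1) requires measurable disease by RECIST 1.1 and does not say that it must lie outside the primary. Cohort A takes "Histologically confirmed, locally advanced, advanced, or metastatic solid tumors"; Cohort B also admits locally advanced disease. ORR by IRC is the primary endpoint (11.5.3.1.1), analysed in all treated patients (11.5.3). Protocol 8.1.4 refers to the SAP for response assessment, but SAP 5.5.1.1 does not say whether the primary can be a target.

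**The concern.** A patient can be admitted because the primary is measurable and then be read by the table for patients who have no target lesion. If that primary shrinks by half and persists, its status is Non-CR/Non-PD and the overall response is SD. The patient stays in the ORR denominator and can become a responder only through CR. Within this subgroup the rule can only lower ORR, the quantity tested in Cohorts A and B.

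There is also a consistency risk. Investigator ORR is a secondary endpoint set beside IRC ORR. If one reader works from the target-lesion bullet and the other from the non-target bullet, the two can differ for reasons unrelated to reading the images.

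**Working it through.** **Trace of one patient.** Locally advanced tumour, measurable primary, no other measurable lesion.

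1. Eligibility (4.1): met, since the disease is measurable.
2. Classification (8.1.3): a target under the target-lesion bullet; non-target under the non-target bullet.
3. If target: the baseline sum is the primary's diameter, Table 12 applies, and a 30% fall gives PR.
4. If non-target: there is no sum, Table 13 applies, and PR is not available.
5. Table 11 does list a PR category for non-target lesions, but it means persistence, and Table 13 carries Non-CR/Non-PD to SD.

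**The plan's own power figures (Protocol 11.1), reproduced by exact binomial.**

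- Cohort B, at least 8 of 35, true ORR 35%: P(X ≥ 8 | 35, 0.35) = 95.8%; stated as about 96%.
- Cohort A, at least 17 of 100, true ORR 25%: P(X ≥ 17 | 100, 0.25) = 97.9%; stated as over 90%. With the stage 1 rule (at least 4 of 35), the sum over x₁ = 4 to 35 of P(X₁ = x₁ | 35, p) × P(X₂ ≥ 17 − x₁ | 65, p) gives 96.9%. The two-stage figure is used below.

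**Illustration 1.** Let f be the share of patients whose only measurable lesion is the primary. The documents do not give f. Assume these patients respond at the same rate as others, none of their responses is a CR, and the target ORRs were set without this rule in mind. The scoreable ORR is then target × (1 − f).

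| f | A: scoreable ORR | A: power | B: scoreable ORR | B: power |
|---|---|---|---|---|
| 0 | 25.0% | 96.9% | 35.0% | 95.8% |
| 5% | 23.75% | 94.6% | 33.25% | 93.5% |
| 10% | 22.5% | 91.1% | 31.5% | 90.3% |
| 20% | 20.0% | 78.4% | 28.0% | 80.5% |

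Power crosses 90% at f = 11.2% (A) and 10.5% (B). With fixed numbers affected, it first falls below 90% at 12 of 100 in Cohort A (89.7%; 11 gives 90.6%) and 4 of 35 in Cohort B (89.9%; 3 gives 91.8%).

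**Illustration 2.** Relax the equal-rate assumption: affected patients respond at half the rate of others, with overall ORR still at target and no CRs. The scoreable ORR is target × (1 − f)/(1 − f/2). At f = 20% the factor is 0.8/0.9, giving 22.2% in A (power 90.1%) and 31.1% in B (power 89.5%).

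**Patients who also have measurable metastases (invented measurements).** The rule changes the target sum, and the result can move either way.

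- Primary 60 to 54 mm, metastases 40 to 26 mm: with the primary, 80/100 − 1 = −20% (SD); without it, 26/40 − 1 = −35% (PR).
- Primary 60 to 36 mm, metastases 40 to 32 mm: with the primary, 68/100 − 1 = −32% (PR); without it, 32/40 − 1 = −20% (SD).

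**The case against.** The strongest reply is that the two bullets do not conflict. The non-target sentence expressly covers a primary that can be measured, so its author foresaw that case and excluded it. A specific rule beside a general one is normally read as an exception, and the preceding bullet already accepts measurable lesions left out of the target set. That reading is natural. A reader might infer that 8.1.3 contradicts itself outright; the text does not establish this, although the exception is not stated as one. But the reading does not help the patient traced above, whose lack of any route to PR is the direct result of applying the exception.

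Second, the primary endpoint is read by the IRC, whose reading rules were not supplied, so nothing shows that the IRC applies this sentence. SAP 5.5.1.1 speaks of target-lesion response in patients with measurable disease at baseline, which hints that such patients are expected to have a target. Both points stand, but the hint is not a rule.

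Third, f could be zero. Cohort A patients must meet "Had disease progression/recurrence after standard treatment for their advanced or metastatic cancer", and Cohort B patients need at least two earlier systemic regimens for advanced or metastatic disease. These criteria do not bound f, but they make a large value harder to credit. Someone looking at the 20% row might infer that the trial is underpowered. The documents do not support that: the row rests on an invented share and on equal response rates, and at half the rate power is back to about 90%.

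**Conclusion.** The gap holds on the text. Applied as written, the always-non-target sentence scores a true partial response as SD whenever the primary is the sole measurable lesion, and neither Table 13 nor the SAP repairs it. It should be corrected, because it touches the primary endpoint and the correction is small.

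Its size is not known. With equal response rates, no CRs and targets set without the rule, power stays at or above 90% up to about 10% affected (91.1% in A, 90.3% in B). At half the response rate, 20% affected gives about 90% in both cohorts. Any CRs among these patients would still count and would soften the loss.

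The conclusion is limited to sole-primary patients. It might be inferred that the rule biases ORR downward across the whole cohort; the worked examples show that it can move a response either way when metastases are also measurable, so no net direction is claimed, and none for type I error.

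**What to change.** Reconcile the two bullets of Protocol 8.1.3 with Table 13 by stating that a measurable primary is a target lesion when it is the only measurable lesion. Carry the same sentence into the SAP and the IRC reading rules, so that IRC and Investigator apply it identically. Merely labelling the present sentence an exception would settle the wording but leave these patients without a route to PR. Deleting it altogether would change target selection for every patient with a measurable primary, and is not needed here.

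For sole-primary patients already enrolled, report how many there are. Keep ORR under the classification used at baseline as primary, and give ORR with the primary as target as a sensitivity analysis, with the target selected from baseline images without sight of follow-up. The reason is that, in an open-label trial, reclassifying these patients can only raise ORR. The order may be reversed only if the rule change is finalised before responses are known.

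The cost is wording in three documents, re-measurement of existing scans for any affected patients, and one extra table. No new scans are needed.

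Two separate editorial points: the 1 mm nodal cut-off in 8.1.3 does not match the 10 mm used elsewhere in 8.1.3 and in Table 11, and the non-target PR row of Table 11 should be labelled Non-CR/Non-PD.

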8.1.4. Response Criteria

Efficacy evaluation will include the assessment of target and non-target responses as well as objective responses. Responses will be assessed as defined in the SAP.

8.1.4.1. Target and Non-Target Response Assessments

Assessments will be based on the definitions for target and non-target lesions described in [Table 11](#).

Table 11: Target and Non-target Lesions

TARGET LESIONS	
Lesions Response:	Definition:
Complete Response (CR)	Disappearance of all target lesions. Any pathological lymph node must have reduction in short axis to <10 mm
Partial Response (PR)	At least a 30% decrease in the sum of diameters of the target lesions, taking as a reference the baseline sum diameters
Progressive Disease (PD)	At least a 20% increase in the sum of diameters of the target lesions, taking as a reference the smallest sum on study, including the baseline sum. In addition to the relative increase of 20%, the sum must also demonstrate an absolute increase of at least 5 mm. Definitive new lesion presence also indicates progression.
Stable Disease (SD)	Neither sufficient shrinkage to qualify for PR nor sufficient increase to qualify for PD, referencing the smallest sum diameters while on study.
NON-TARGET LESIONS	
Lesions Response:	Definition:
Complete Response (CR)	Disappearance of all non-target lesions and normalization of tumor marker level. All lymph nodes must be non-pathological in size (<10-mm short axis)
Partial Response (PR)	Persistence of one or more non-target lesion(s) and/or maintenance of tumor marker level above the normal limits
Progressive Disease (PD)	Unequivocal progression of existing non-target lesions (see following definition).

Abbreviations: CR=complete response; PD=progressive disease; PR=partial response; SD=stable disease

Progression in Non-target Disease: There must be an overall level of substantial worsening in non-target disease such that, even in the presence of SD or PR in target disease, the overall tumor burden has increased sufficiently to merit discontinuation of therapy.

8.1.4.2. Additional Criteria to Consider When Making Response Assessments

Because worsening in non-target disease cannot be easily quantified, a useful test that can be applied when assessing patients for unequivocal progression is to consider if the increase in overall disease burden based on the change in non-measurable disease is comparable in magnitude to the increase that would be required to declare PD for measurable disease (ie, an increase in tumor burden representing an additional 73% increase in “volume” [which is equivalent to a 20% increase in the diameter of a measurable lesion]).

When effusions are known to be a potential adverse effect of treatment, cytological confirmation of the neoplastic origin of any effusion that appears or worsens during treatment when the measurable tumor has met criteria for response or SD is not mandatory, but might be performed to differentiate between response (or SD) and PD when substantial change of effusion and or ascites is noted.

If a patient is discontinued from the study before PD occurs and receives local or regional palliative radiotherapy during the follow-up period, the irradiation site must be omitted from the response assessment of the patient; however, if the site is observed to demonstrate disease progression, this case should be judged as PD.

For equivocal findings of progression (eg, very small and uncertain new lesions; cystic changes or necrosis in existing lesions), treatment may continue until the next scheduled assessment. If at the next scheduled assessment, progression is confirmed, the date of progression should be the earlier date when progression was suspected.

8.1.5. Objective Response Assessment

Assessments will be based on the definitions provided in [Table 12](#) and [Table 13](#). Since this is a non-randomized study, all responses (CR/PR) must be confirmed.

Table 12: Time Point Response for Patients with Target (\pm Non-target) Disease

Target Lesions	Non-Target Lesions	New Lesions	Objective Response
CR	CR	No	CR
CR	Non-CR/Non-PD or Not all evaluated	No	PR
PR	Non-PD or Not all evaluated	No	PR
SD	Non-PD or Not all evaluated	No	SD
Not all evaluated	Non-PD	No	NE
PD	Any	Yes or No	PD
Any	PD	Yes or No	PD
Any	Any	Yes	PD

Abbreviations: CR=complete response; NE=not evaluable; PD=progressive disease; PR=partial response; SD=stable disease

Table 13: Time Point Response for Patients with Only Non-target Disease

Non-Target Lesions	New Lesions	Objective Response
CR	No	CR
Non-CR/Non-PD	No	SD
Not all evaluated	No	NE
Unequivocal PD	Yes or No	PD
Any	Yes	PD

Abbreviations: CR=complete response; NE=not evaluable; PD=progressive disease; PR=partial response; SD=stable disease

8.2. Cohort C

8.2.1. Efficacy Criteria

Efficacy will be assessed by evaluation of:

- Bone marrow histomorphology changes, standard cytogenetics, and *FGFR* molecular status
- Peripheral blood assessment (blood count) including potentially *FGFR* molecular status
- Positron emission tomography (PET) scan for fluorodeoxyglucose (FDG) avid lesions
- Imaging (CT/MRI) in case of presence of solid lesions
- Clinical assessment

If the Investigator determines that a patient has developed clinical disease progression manifested by symptomatic deterioration, the patient may stop treatment. Every effort should be made to document objective disease progression even after discontinuation of treatment.

